**STATISTICS AND ANALYSIS**

### **12.1. The Number of Participants**

This is a pilot study that aims at investigating a possible relation between scar location and AHR to MPP more than proving a statistical significant different between AHR to MPP in the peri-scar region compared to the remote myocardium. Therefore, a small sample size of 15 patients has been chosen just in order to confirm the validity of the study hypothesis to be further investigated in a bigger study.

Of note, a recent study (13) has documented a variable AHR to MPP over single-site LV pacing with a percentage increase in LV-dP/dT between 0% and 40% according to LV site. If our hypothesis is confirmed and the best and worst MPP sites correspond to peri-scar and remote-myocardium respectively, 15 patients could be also enough in order to show a statistically significant difference between the two sites with a 95% confidence level and a 80% power.

### **12.2. Description of Statistical Methods**

Comparison of response to the two different pacing sites will be made using appropriate statistical testing. We would expect the data to be normally distributed, in which case T-tests will be used.

### **12.3. Analysis of Outcome Measures**

The following measurements will be collected and analysed:

- LV-dP/dTmax during spontaneous ventricular rhythm;
- LV-dP/dTmax during single site LV pacing in 4 different pacing configurations (4 different poles used in turn), with the LV lead either in the peri-scar CS branch or in the remote myocardium CS branch. The pacing configuration producing the biggest LV-dP/dTmax over spontaneous ventricular rhythm will be considered the best pacing configuration in each CS branch and used for further comparisons and analyses;
- LV-dP/dTmax during single MPP LV pacing in 3 different configurations, with the LV lead either in the peri-scar CS branch or in the remote myocardium CS branch. The pacing configuration producing the biggest LV-dP/dTmax will be considered the best pacing configuration in each CS branch and used for further comparisons and analyses.

|  |                                    |                                      |
|--|------------------------------------|--------------------------------------|
| Subject: Research protocol                    | Short Title: SCAR MPP study | Chief Investigator: [name] |
| Version/Date: 1.1 /6 th April 2019 | IRAS Ref: 211326            | Ethics Ref: 16/SC/0662        |

The percentage change in LV-dP/dTmax produced by the best single site LV pacing configuration over spontaneous ventricular rhythm will represent the best Acute Haemodynamic Response (AHR) of single site LV pacing in each CS branch. The percentage change in LV-dP/dTmax produced by the best MPP LV pacing configuration over spontaneous ventricular rhythm will represent the best Acute Haemodynamic Response (AHR) of MPP LV pacing in each CS branch.

The following comparisons will be made as outcome measures:

- AHR produced by the best MPP configuration in the peri-scar region versus AHR produced by best MPP configuration in the remote myocardium;
- percentage increase of LV-dp/dTmax produced by the best MPP configuration over single site LV pacing in the peri-scar region versus percentage increase of LV-dp/dTmax produced by the best MPP configuration over the best conventional single-site LV pacing in the remote myocardium.

Our hypotheses are that:

- the AHR produced by the best MPP configuration will be consistently and statistically significantly higher in the peri-scar region compared to the remote myocardium;
- the percentage increase of LV-dp/dTmax produced by the best MPP configuration over single-site LV pacing will be consistently and statistically significantly higher in the peri-scar region compared to the remote myocardium.

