3. A three-dimensional electroanatomical map of the CS venous system will be constructed with Precision mapping system and a Biotronik Vision wire (Biotronik Se & Co. KG, Berlin, Germany) by using the CS venogram as a guide. The map will be merged with the correspondent cardiac MRI images in order to locate the myocardial scar in respect to the CS branches. This will allow the identification of two target CS branches for the study measurements, one located in the peri-scar region and one located in the remote myocardium.

4. A Certus PressureWire will be then introduced into the LV. A PhysioMon software (Radi Medical Systems, Uppsala, Sweden) will be used for electronic calculation of the LV-dP/dTmax from every heartbeat for a period of at least thirty seconds to ensure steady-state conditions. The baseline LV-dP/dTmax will be measured during ventricular spontaneous rhythm.

A St. Jude Medical quadripolar left ventricular lead will be sequentially placed in the “peri-scar” CS branch and in the “remote myocardium” CS branch. In each site the percentage increase in LV-dP/dTmax (Acute Haemodynamic Response, AHR) produced by both conventional single-site and MPP LV pacing to will be measured. All 4 poles of the quadripolar lead will be used in turn for conventional single-site LV pacing, 3 different configurations will be used in turn for MPP. The LV-dP/dTmax will be recorded for each pacing configuration in order to identify the MPP and the single-site LV pacing configurations producing the best AHR (best percentage increase of LV-dP/dTmax).

The AHR produced by the best MPP configuration in peri-scar region will be compared with the AHR produced by the best MPP configuration in the remote myocardium. Moreover, the percentage increase of LV-dP/dTmax produced by the best MPP configuration over the best conventional single-site LV pacing in the peri-scar region will be compared with the same measurement obtained in the remote myocardium.

The decision about the final position of the LV lead and the activation of MPP feature after the CRT implant will be left to operator preference. This is usually decided on the basis of minimum pacing output required to achieve capture, lead stability and ECG changes suggestive of good resynchronization.

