The  $LV-dP/dT_{max}$  will be measured during spontaneous ventricular rhythm. A St. Jude Medical quadripolar left ventricular lead (Quartet 1458Q or newer) will be then sequentially placed in the “peri-scar” CS branch and in the “remote myocardium” CS branch and the  $LV-dP/dT_{max}$  will be measured during conventional single-site and MPP LV pacing in each site. In each site the AHR to both conventional single-site and MPP LV pacing will be performed by measuring the percentage change in  $LV-dP/dT_{max}$  compared to spontaneous ventricular rhythm. Different single-site (all 4 poles in turn) and MPP (3 configurations) LV pacing settings will be tested to this aim in order to identify the best MPP and single-site LV pacing configurations.

The AHR produced by the best MPP configuration in peri-scar region will be compared with the AHR produced by the best MPP configuration in the remote myocardium. Moreover, the percentage increase of  $LV-dP/dT_{max}$  produced by the best MPP configuration over the best conventional single-site LV pacing in the peri-scar region will be compared with the same measurement obtained in the remote myocardium.

All measurements will be repeated at least twice in order to make sure they are reliable and reproducible. The pressure wire and the sheath will be removed after all measurements are complete.

Data will be electronically captured from the pressure wire and automatically extracted on an excel database.

The  $LV-dP/dT_{max}$  measurements will not influence the operator’s decision about the final position of the LV lead. This will be dictated, as standard practice, by minimum pacing output required to achieve capture, lead stability and ECG changes suggestive of good resynchronization.

All subjects will be implanted with a regulatory approved St. Jude Medical CRT device compatible with MPP feature (models n° CD3271-40(Q), CD3371-40(Q), CD3371-40C(QC) or newer).

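### Does section 12.3 set MPP against a weaker single-site comparator in the peri-scar region than in the remote myocardium?

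*Combined protocol and SAP*

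**What the plan says.** The second comparison listed in section 12.3 concerns the percentage gain in LV-dP/dTmax from MPP over single-site pacing, peri-scar against remote. Its first half reads "produced by the best MPP configuration over single site LV pacing in the peri-scar region versus percentage increase". Its second half reads "produced by the best MPP configuration over the best conventional single-site LV pacing in the remote myocardium". The word for best is attached to the single-site comparator in the remote region only.

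The same section has already fixed how the single-site value is chosen. Four poles are tested in each branch, and the one giving the largest LV-dP/dTmax "will be considered the best pacing configuration in each CS branch and used for further comparisons and analyses". It then defines a best single-site response for each branch.

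Section 5 states the comparison as best MPP "over the best conventional single-site LV pacing in the peri-scar region will be compared with the same measurement obtained in the remote myocardium". Section 9.2.4 gives the same definition: "produced by the best MPP configuration over the best conventional single-site LV pacing in the peri-scar region will be compared with the same measurement". The second hypothesis at the end of section 12.3 uses a shorter phrase, "produced by the best MPP configuration over single-site LV pacing will be consistently and statistically significantly higher in the peri-scar region", applied once to both regions. The outcome wording in sections 1 and 6 is shorter still and omits best for MPP as well.

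**The concern.** The listed comparison is where an analyst would look first, and it appears to use two comparators. If the remote gain is taken over the best of four poles and the peri-scar gain over something less, the peri-scar region starts ahead even when MPP does nothing in either region. The maximum of several noisy values exceeds their average, so the error would run toward the hypothesis.

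The outcome matters. The primary objective is the added benefit of MPP over single-site pacing, and this is the outcome that measures it directly. The other one, the response to MPP over spontaneous rhythm, does not separate MPP from single-site pacing. Section 12.3 also anticipates a statistically significant result, and with 15 patients a bias of a few percentage points could produce one.

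**Working it through.** **1. The definitions side by side**

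| Place | Peri-scar comparator | Remote comparator |
|---|---|---|
| 12.3, rule for choosing the configuration | best of 4 poles | best of 4 poles |
| 12.3, second listed comparison | single-site, not qualified | best single-site |
| 12.3, second hypothesis | single-site, not qualified | single-site, not qualified |
| 5, item 4 | best single-site | the same measurement |
| 9.2.4 | best single-site | the same measurement |
| 1 and 6, outcome wording | single-site, not qualified | single-site, not qualified |

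Only one row is asymmetric, and it is silent on the peri-scar pole; it does not name a different one. The rule in the first row fills that silence, and sections 5 and 9.2.4 confirm it. Nowhere does the protocol mention a mean of poles, a pre-chosen pole or any other alternative.

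**2. The symmetric reading with no true effect**

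From the documents: n = 15, both regions measured in each patient, and 4 single-site and 3 MPP configurations per branch ("Different single-site (all 4 poles in turn) and MPP (3 configurations) LV pacing settings will be tested"). Assumed, because the documents give no variability: paced LV-dP/dTmax at 115% of intrinsic, branch SD 5 points, and pole-to-pole SD s of 1, 2, 3 or 5 points. The test is a paired t-test, two-sided at 0.05, over 20,000 simulated trials.

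Gain in a branch = 100 × (best MPP / single-site reference − 1). With the best of 4 as reference in both regions, the mean peri-scar minus remote difference is about 0.0 and the false-positive rate is 4.9% to 5.2%. Choosing from 3 MPP settings but 4 poles causes no bias here, because the imbalance is the same in both regions and cancels.

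**3. What the literal sentence would cost**

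The expected maximum of 4 independent normal values exceeds their mean by 1.03 SD. On a base of 115%, the approximate bias is 1.03 × s / 1.15 = 0.90 × s.

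| s | Peri-scar uses mean of 4 | Peri-scar uses one fixed pole |
|---|---|---|
| 1 | +0.9 points | +0.9 points |
| 2 | +1.8 | +1.8 |
| 3 | +2.7 | +2.7 |
| 5 | +4.4 | +4.6 |
| False-positive rate | 77–78% | 64–65% |

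Both peri-scar rules in this table had to be invented, since the protocol contains neither.

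**4. How firm those error rates are**

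In the model of step 3, patient and branch effects almost cancel in the ratio. Pole spread is then nearly the only noise, and bias and noise grow together. Section 12.1 cites gains that range from 0% to 40% by LV site, so real variation in the MPP gain should be expected. Adding mean-zero variation by patient and site to the percentage gain (branch SD 4, mean of 4 poles in the peri-scar region) gives these false-positive rates:

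| SD of gain (points) | s = 3 | s = 5 |
|---|---|---|
| 0 | 78% | 78% |
| 3 | 42% | 60% |
| 5 | 23% | 41% |
| 10 | 10% | 18% |

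At s = 1 and a gain SD of 3, the rate is 11%. The bias in points is unchanged by this variation, but the error rate depends heavily on it.

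**The case for a change.** The strongest case for a change is that a general rule does not automatically override a specific outcome definition. The listed comparison writes best for one region and leaves it out for the other. An analyst could follow that sentence to the letter and claim compliance, and a later reader could not prove from it alone which comparator was prespecified. Section 12.2 adds only a reference to t-tests. The misreading would favour the hypothesis on the outcome closest to the primary objective.

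Some of this stands. The wording is uneven, and a one-sided use of a weaker comparator would be a serious bias. What does not stand is the step from there to a biased plan. The literal reading requires setting aside an instruction in the same section and two explicit definitions elsewhere, and then supplying a peri-scar rule that the protocol never gives. The shorter wording in sections 1 and 6 and in the hypothesis treats both regions alike, so it creates no asymmetry. The first listed comparison, best MPP response in each region, is worded symmetrically and is unaffected. Section 12.1 also presents the study as a pilot that explores a relation more than it tests for significance.

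**Conclusion.** No change to the plan follows. Read as a whole, the protocol already specifies best MPP over best single-site pacing in both regions, with a bias of about 0 and a false-positive rate of about 5% when there is no effect. The missing words in one half of one sentence are a clerical slip. Restoring them would be tidy but would alter no measurement, comparison or conclusion.

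The bias of about 0.9 times the pole-to-pole SD, and the false-positive rates of 64% to 78%, belong only to a reading that the protocol does not support. Those rates also assume that the MPP gain does not vary between patients and sites. With such variation they fall, to about 10% at a pole SD of 3 and a gain SD of 10. All of these sizes rest on assumed SDs. The conclusion rests on the text and does not depend on them.

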## **13. DATA MANAGEMENT**

### **13.1. Access to Data**

Direct access will be granted to authorised representatives from the Sponsor or host institution for monitoring and/or audit of the study to ensure compliance with regulations.

### **13.2. Data Recording and Record Keeping**

- The study staff will ensure that the participants' anonymity is maintained.
- NHS code of confidentiality will be followed.
- Personal data will be anonymised with the use of a study participant number. The study number will be correlated with personal data about the patient in one electronic file, which will be individually password protected and secured as above.
- All electronic records (excel databases) will be stored on a NHS server within password-protected user accounts and they will be anonymized.
- The MRI scans will be stored in the usual manner on the OCMR server.
- The file linking personal data to the study ID will be stored separately to the study data.
- Paper records will be stored in a locked filing cabinet to which only the research team have access. The study will comply with the Data Protection Act which requires data to be anonymised as soon as it is practical to do so.

|  |                                    |                                      |
|--|------------------------------------|--------------------------------------|
| Subject: Research protocol                    | Short Title: SCAR MPP study | Chief Investigator: [name] |
| Version/Date: 1.1 /6 th April 2019 | IRAS Ref: 211326            | Ethics Ref: 16/SC/0662        |

- EP data analysis will be performed by [name] and [name] in the JR hospital. No further data transfer will be performed.
- As per Trust Policy, after the end of the trial period, all study data will be kept for a further period of 5 years before being deleted, to allow for full analysis and results publication. Personal data will be only kept for a few months after the study has finished, before being destroyed.

## **14. ETHICAL AND REGULATORY CONSIDERATIONS**

### **14.1. Declaration of Helsinki**

The Investigator will ensure that this study is conducted in accordance with the principles of the Declaration of Helsinki.

### **14.2. Guidelines for Good Clinical Practice**

The Investigator will ensure that this study is conducted in accordance with relevant regulations and with Good Clinical Practice.

### **14.3. Approvals**

The protocol, informed consent form, participant information sheet and any proposed advertising material will be submitted to an appropriate Research Ethics Committee (REC), and host institution(s) for written approval.

The Investigator will submit and, where necessary, obtain approval from the above parties for all substantial amendments to the original approved documents.

### **14.4. Reporting**

The CI shall submit once a year throughout the study or, on request, an Annual Progress report to the REC Committee, host organisation and Sponsor. In addition, an End of Study notification and final report will be submitted to the same parties.

### **14.5. Participant Confidentiality**

The study staff will ensure that the participants' anonymity is maintained. The participants will be identified only by initials and a participants ID number on the CRF and any electronic database. All documents will be stored securely and only accessible by study staff and authorised personnel. The study will comply with the Data Protection Act, which requires data to be anonymised as soon as it is practical to do so.

Participants anonymity will be maintained and no patient identifiable information will be published.

### **14.6. Expenses and Benefits**

|  |                                    |                                      |
|--|------------------------------------|--------------------------------------|
| Subject: Research protocol                    | Short Title: SCAR MPP study | Chief Investigator: [name] |
| Version/Date: 1.1 /6 th April 2019 | IRAS Ref: 211326            | Ethics Ref: 16/SC/0662        |

Reasonable travel expenses for any visits additional to normal care will be reimbursed on production of receipts, or a mileage allowance provided as appropriate.

We intend that the majority of study visits will be performed at the time of routine clinical visits to hospital so would not expect that patients will have to make many extra visits to hospital.

Light refreshments will also be available.

#### **14.7. Other ethical considerations**

No other ethical considerations are involved in this study.

### **15. FINANCE AND INSURANCE**

#### **15.1. Funding**

This research study was selected for the NIHR Oxford Biomedical Research Centre (BRC) Young investigator Award in 2015 and will be supported by the corresponding research grant awarded. Any shortfalls will be covered by the CRM Hub.

#### **15.2. Insurance**

NHS bodies are legally liable for the negligent acts and omissions of their employees. If you are harmed whilst taking part in a clinical research study as a result of negligence on the part of a member of the study team this liability cover would apply.

Non-negligent harm is not covered by the NHS indemnity scheme. The Oxford University NHS Trust, therefore, cannot agree in advance to pay compensation in these circumstances.

In exceptional circumstances an ex-gratia payment may be offered.

### **16. PUBLICATION POLICY**

The Investigators will be involved in reviewing drafts of the manuscripts, abstracts, press releases and any other publications arising from the study. Authorship will be determined in accordance with the ICMJE guidelines and other contributors will be acknowledged. For participants who have stated they wish to receive a copy of the research results, a copy of these results will be sent by post.

[figure not shown]
|  |                                    |                                      |
|--|------------------------------------|--------------------------------------|
| Subject: Research protocol                    | Short Title: SCAR MPP study | Chief Investigator: [name] |
| Version/Date: 1.1 /6 th April 2019 | IRAS Ref: 211326            | Ethics Ref: 16/SC/0662        |

## 18. APPENDIX A: STUDY FLOW CHART

|   |                             |                               |
|---|-----------------------------|-------------------------------|
| Subject: Research protocol                    | Short Title: SCAR MPP study | Chief Investigator: [name] |
| Version/Date: 1.1 /6 th April 2019 | IRAS Ref: 211326            | Ethics Ref: 16/SC/0662        |
| Page 25 of 27                                 |                             |                               |

**19. APPENDIX B: SCHEDULE OF TIMING OF STUDY APPOINTMENTS AND STUDY PROCEDURES**

|   | Recruitment | Baseline visit | Study intervention | Pre-discharge review |
|---|-------------|----------------|--------------------|----------------------|
| Time since CRT-D implant procedure       | ≥ 6 wks     | - 1-2 wks      | 0                  | + 1 d                |
| Study procedures                  |             |                |                    |                      |
| Eligibility assessment                   | X           | X              |                    |                      |
| Patient's information                    | X           |                |                    |                      |
| Informed consent                         |             | X              |                    |                      |
| Demographics                             |             | X              |                    |                      |
| Medical history                          |             | X              |                    | X                    |
| Cardiac MRI                              |             | X              |                    |                      |
| CRT-D implant                            |             |                | X                  |                      |
| 3D map of CS venous system               |             |                | X                  |                      |
| Acute haemodynamic response measurements |             |                | X                  |                      |

d = day; f-up = follow-up; wks = weeks.

|  |                                    |                                      |
|--|------------------------------------|--------------------------------------|
| Subject: Research protocol                    | Short Title: SCAR MPP study | Chief Investigator: [name] |
| Version/Date: 1.1 /6 th April 2019 | IRAS Ref: 211326            | Ethics Ref: 16/SC/0662        |
| Page 26 of 27                                 |                                    |                                      |

